7.4.2 Analysis of Non-Vaccine-Type (NVT) Pneumococcal Immunogenicity

In both Stage 1 Group 1 and Stage 2 Group 2, blood draws to determine SP1500+0785 levels (ng/mL) will be collected for subjects given either ASP3772 or PCV13. Levels of TH17 will be determined using an ELISpot assay and IL17 will be measured using a standard MSD ELISA. Levels of the following cytokines will also be assayed: IL-17, IL-22, CCI [REDACTED]. Summaries of the levels at baseline, Day 7 and Day 30 will be provided. The fold increase relative to baseline at Days 7 and 30 will also be summarized. Paired comparisons between each of the ASP3772 dose levels and PCV13 will be completed using a Wilcoxon Test. These comparisons will be made for subjects in Stage 1, Group 1 and separately for subjects in Stage 2, Group 2.

7.4.3 Dose Response

CCI

CCI

7.4.4 Analysis of Biotin and Anti-Biotin

Samples for anti-biotin antibodies will be collected before immunization, at Day 30 and if positive at Day 30, at Day 180 for subjects in Stage 1, Group 1 and Stage 2, Group 2. Biotin levels will be measured in the same sample if the sample is positive for anti-biotin.

Paired comparisons between each of the ASP3772 dose levels and PCV13 will be completed using a Wilcoxon Test. These comparisons will be made for subjects in Stage 1, Group 1 followed by subjects in Stage 2, Group 2.

7.5 Analysis of Safety

All analysis of safety will be presented by treatment group (ASP3772 (1 µg, 2 µg, 5 µg) or PCV13) and stage for SAF. All adult subjects who receive PCV13 will be combined into a single group and all elderly subjects who receive PCV13 will be combined into a single group. Safety data for subjects given PPSV23 will not be compared with any other treatment group since these subjects were not a randomized treatment group.

7.5.1 Adverse Events

AEs will be coded using the Medical Dictionary for Regulatory Activities (MedDRA). An overview table will include the following:

- Number and percentage of subjects with TEAEs
- Number and percentage of subjects with drug related TEAEs
- Number and percentage of subjects with serious TEAEs
- Number and percentage of subjects with serious drug related TEAEs
- Number of subjects with medically attended TEAEs (MAAEs)
- Number of subjects with potential immune mediated TEAEs (PIMMCs)
- Number of subjects with new onset chronic disease TEAEs (NOCDs)
- Number of deaths.

The number and percentage of subjects with TEAEs, classified by SOC, and PT will be summarized. Summaries (number and percentage of subjects) with each specific type of TEAE classified by SOC and preferred term will be provided for the following:

- TEAEs
- Drug-Related TEAEs,
- Serious TEAEs,
- Drug-Related serious TEAEs,
- TEAEs by Severity
- TEAEs leading to permanent discontinuation of study drug,
- Medically attended TEAEs (MAAEs)
- Potential immune mediated TEAEs (PIMMCs)
- New onset chronic disease TEAEs (NOCDs)
- Deaths

- Common (>=5% in any treatment group) Treatment-Emergent Adverse Events excluding Serious Adverse Events
- If a subject has multiple TEAEs with the same SOC or PT, the subject will be counted only once for the SOC and for an individual preferred term. For summaries by relationship, but with differing relationship (Yes, No), the subject will be counted only once for events with relationship equal to 'Yes'. If any of the relationship values are missing then the subject will be counted as having a related AE. A subject will be counted once under maximum severity. If severity is missing for all episodes of the event, the subject will be counted under the Missing category. Serious Adverse Events should not only include SAEs identified by the investigator on the eCRF, but also AEs upgraded by the Sponsor based on the Always Serious List (SAE flag on eCRF may not always be updated, but there will always be an SAE number in the eCRF database).

The following adverse events of special interest are defined:

- Reactogenicity

Each local and systemic solicited reaction that continues beyond the first 7 days after the immunization or if it is serious will be recorded as an adverse event. The percentage of subjects who report pain, tenderness, redness/erythema, swelling or hardness/induration at the vaccination site, nausea, vomiting, diarrhea, headache, tiredness (fatigue), myalgia/muscle pain and arthralgia or other AE (not specified) will be summarized by grade (n, %) and overall regardless of grade (n,%).

Reactogenicity for each dose of ASP3772 will be compared to PCV13. The percentage of subjects who had 0, 1, 2, 3, 4 or 5 local reactions using a nonparametric CMH rank statistic. The systemic reactions will be compared in a similar way. The severity for each type of reaction will be compared for each dose of ASP3772 to PCV13 after assigning an increasing score to each severity and comparing the severity using a CMH statistic with scores=modridit.

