Stage 2 of the study is a dose-finding (sequentially higher doses), active-controlled, observer-blinded study with a 3:1 randomization (ASP3772:PCV13) in elderly subjects 65 to 85 years of age (Group 2). For Stage 2, Group 2 subjects the vaccine administrator will differ from the person evaluating reactogenicity to remove reporting bias for these events. Treatment assignment will also be unknown to the blinded study team.

After screening, PCV13 naïve subjects will be randomized within each cohort to receive ASP3772 or PCV13. Subjects randomized to ASP3772 will receive a single dose of ASP3772 administered as a 0.5 mL intramuscular (IM) injection on day 1, at 1 of 3 dose levels: 1, 2 or 5 µg of ASP3772 for Cohorts 4, 5 and 6, respectively. The subjects randomized to PCV13 will receive a single injection of the standard dose of PCV13.

Stage 2 will commence after the DEC has evaluated safety (including reactogenicity) data through 30 days from all cohorts in Stage 1. Dose escalation to Cohort 5 (intermediate dose, 2 µg) in Stage 2 will commence once the DEC has evaluated Stage 2 Cohort 4 (1 µg) safety (including reactogenicity) and tolerability through 7 days postimmunization. Dose escalation into Cohort 6 (high dose, 5 µg) in Stage 2 will commence once the DEC has evaluated Stage 2 Cohort 5. The DEC will review the data for each cohort in Stage 2, Group 2 in a blinded manner. The DEC Charter will provide details for revealing the treatment assignment for individual subjects to DEC members, if necessary. Randomization for Stage 2 subjects will be stratified by age (65 to 74 years of age and 75 to 85 years of age) to ensure there is a balanced number of subjects within each age cohort immunized with either ASP3772 or PCV13.

Safety and tolerability assessments including adverse events (AEs) will continue through 30 days postimmunization. Safety assessments for SAEs and MAAEs including PIMMCs and NOCDs will continue through day 180 postimmunization. Data will be collected in an observer-blinded manner (vaccine recipients and the site staff who are responsible for evaluation of any study endpoint will be unaware of which vaccine the subject received).

Serum samples to measure IgG and OPA will be collected prior to study vaccination on day 1 and postimmunization on day 30. The primary immunogenicity evaluation for dose finding is 30 days following the initial immunization.

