3.3 Randomization

A central randomization will be used for this study. Stage 1 subjects will be randomized to receive either ASP3772 (1, 2 or 5 µg) or PCV13 with a 3:1 ratio.

Stage 2, Group 2 subjects will be randomized to receive either ASP3772 (1, 2 or 5 µg) or PCV13 with a 3:1 ratio. The randomization for Group 2 will be stratified by age (65 to 74 years of age and 75 to 85 years of age).

The randomization assignment for Stage 1 and Stage 2, Group 2 will be unavailable to anyone involved with the study with the exception of the pharmacist and vaccine administrator until all Day 30 visits have been completed. After all subjects in Stage 1 have completed Day 30, there will be a data cutoff and an interim analysis. Similarly, once all Day 30 visits for subjects in Stage 2, Group 2 have completed, there will be a data cutoff and interim analysis. Additional safety information will be collected at the Day 180 visit.

Stage 2, Group 3 subjects will have been previously given PCV13 before entering the study and will be enrolled to receive a booster vaccination with PPSV23 only on Day 1.

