8 REVISION AND RATIONALE

Version 1 of the SAP has been updated to include planned interim analyses, provide greater details of treatment assignment blinding for study personnel, update the analysis of exploratory endpoints and to correct assorted typographical errors.

Version 2 of the SAP has been updated to

1. Increased screening for Stage 2 to be consistent with the protocol from -28 days to -40 days.
2. Added: “Subjects who are given PPSV23 without previous exposure to PCV13 will not be included in the immunogenicity summaries.” These are subjects in Stage 2, Group 3 who should have received PCV13 before receiving PPSV23.
3. **CCI** [REDACTED]
4. Changed the algorithm for setting the value for LLOQ for the calculation of fold change in response to feedback from the FDA. Values below the LLOQ will be set to $\frac{1}{2}$ LLOQ for calculation of geometric means and set to LLOQ for calculation of fold changes.
5. **CCI** [REDACTED]
6. **CCI** [REDACTED]
7. Added a CMH rank test to examine the difference between ASP3772 and PCV13 in the number of reactogenicity reactions. Added a CMH statistics with scores=modridit to compare the severity for each type of reaction between each dose of ASP3772 and PCV13 after assigning an increasing score to each severity.
8. Added details for determining systemic reactogenicity events during the 1st hour post vaccination.

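### The Stage 2 reactogenicity CMH tests name no stratification variable; specify the age stratum used in randomisation (a small, low-cost improvement)

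*SAP*

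**What the plan says.** SAP 7.5.1 compares reactogenicity for each ASP3772 dose with PCV13 in two ways. The first concerns the number of local reactions: "The percentage of subjects who had 0, 1, 2, 3, 4 or 5 local reactions using a nonparametric CMH rank statistic". Systemic reactions are handled similarly. The second assigns increasing scores to severity for each type of reaction, "comparing the severity using a CMH statistic with scores=modridit". No stratification variable is given for either. The revision note in SAP section 8 that introduced the tests gives none either: "Added a CMH rank test to examine the difference between ASP3772 and PCV13 in the number of reactogenicity reactions".

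Three other places bear on this:

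- SAP 3.3: "The randomization for Group 2 will be stratified by age", with strata 65-74 and 75-85 years. SAP 7.4.1 includes the same two-level age factor in the ANCOVA of log OPA titres and log IgG.
- SAP 7.5: "all elderly subjects who receive PCV13 will be combined into a single group".
- SAP 3.2: cohorts are recruited one after another. "Dose escalation to Cohort 5 (intermediate dose, 2 µg) in Stage 2 will commence once the DEC has evaluated Stage 2 Cohort 4"; Cohort 6 follows in the same way.

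SAP 7.1 allows safety summaries by elderly age group where they are called for, but 7.5.1 and 7.5.2 do not call for them for reactogenicity.

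**The concern.** A CMH statistic is designed to combine evidence over strata. With no stratum named, a programmer working from the text would produce a plain two-way table, and the randomisation factor would drop out of the comparison.

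Stratified randomisation balances age between ASP3772 and PCV13 inside each cohort. It does not balance age between one cohort's ASP3772 arm and a PCV13 group of which two thirds come from the other cohorts. The documents set no quota for the age share of a cohort. If cohorts differ in age mix and reaction rates differ by age, part of the age effect would appear as a vaccine difference.

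Reactogenicity is among the primary safety endpoints, and these CMH tests are its only specified between-group tests. A modest loss of precision is also at stake if age predicts reactions.

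**Working it through.** **Inputs from the documents.** Stage 2 Group 2 has three cohorts of 99 ASP3772 and 33 PCV13 (SAP 3.2). The default is a two-sided test at 0.05 (SAP 7.1). The documents give no age mix by cohort and no reaction rates by age, so every share and rate below is an assumption.

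**Step 1: the plan's own figure.** 3 × (99 + 33) = 396, as stated. Pooled PCV13 is 3 × 33 = 99, so each dose comparison is 99 versus 99.

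**Step 2: how much of an age shift carries over.** One third of pooled PCV13 (33 of 99) comes from the dose's own cohort and has the same age mix by design. So the share gap is 2/3 × (shift from the other two cohorts). A 10-point gap needs a 15-point shift; a 20-point shift leaves a 13.3-point gap.

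**Step 3: bias for one yes/no reaction.** Bias = share gap × difference in reaction rate between age strata.

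- Central: 0.10 × 0.15 = 1.5 points
- Low: 0.05 × 0.10 = 0.5 points
- High: 0.15 × 0.20 = 3.0 points

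**Step 4: compare with sampling error.** At a reaction rate near 50%, SE = √(2 × 0.5 × 0.5 / 99) = 7.1 points. The central bias is 1.5 / 7.1 = 0.2 SE. With no true effect, the rejection rate is Φ(b/SE − 1.96) + Φ(−b/SE − 1.96), which is about 0.055 for 1.5 points and about 0.07 for 3 points.

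**Step 5: chance imbalance only.** If the expected share aged 65-74 is 70% in every cohort of 132, the SD of the gap is √(0.7 × 0.3 / 132 × 2/3) = 3.3 points. In simulation, 95% of gaps lie within 6.3 points. The bias is then at most about 0.063 × 0.15 = 0.9 points, or 0.063 × 0.20 = 1.3 points at a 20-point rate difference.

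**Step 6: the 0-5 count.** The CMH rank test was simulated with modified ridits, no true vaccine effect, Cohort 6 versus pooled PCV13, and five reactions with correlation 0.3. There were 3,000 runs per row, with a simulation error of about 0.004.

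| Share aged 65-74, cohorts 4/5/6 | Rate per reaction, 65-74 vs 75-85 | Unstratified | Age-stratified |
|---|---|---|---|
| 70/70/70% | 0.60 vs 0.40 | 0.036 | 0.043 |
| 70/70/60% | 0.60 vs 0.40 | 0.048 | 0.045 |
| 70/70/50% | 0.55 vs 0.45 | 0.062 | 0.054 |
| 70/70/50% | 0.60 vs 0.40 | 0.078 | 0.046 |
| 80/80/40% | 0.60 vs 0.40 | 0.194 | 0.054 |
| 80/80/40% | 0.70 vs 0.40 | 0.349 | 0.050 |

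The count is more sensitive than a single reaction: in the fourth row the yes/no approximation gives 0.066. The last two rows need a share gap of 40 − (80 + 80 + 40)/3 = −26.7 points, well beyond the range in step 3.

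**Step 7: precision.** With equal age mix, rates of 0.50 vs 0.30 by age and a true 15-point vaccine effect (2,000 runs), power is 0.88 unstratified and 0.90 age-stratified.

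**Step 8: what age stratification does not do.** With equal age mix but Cohort 6 rates 10 points higher in both arms, rejection is 0.277 unstratified, 0.285 age-stratified and 0.055 stratified by age and cohort. Strata that hold only PCV13 contribute nothing, so the last version in effect compares 99 with 33 concurrent controls. In the setting of step 7 its power is 0.62.

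**The case against.** The strongest reply is that the SAP is silent, not wrong. A reader might infer that the sponsor decided to ignore age. The documents do not support that: neither 7.5.1 nor section 8 says the tests are unstratified, and the sentence on reaction counts is itself incomplete. This part stands, and the point is therefore one of specification.

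A reader might also infer that the primary safety comparison is materially biased. That would need a systematic recruitment shift between cohorts together with age-dependent reaction rates. The documents show neither, and one set of eligibility criteria covers all of Stage 2. Protocol 7.3 summarises age by dose cohort, by immunization group and for all PCV13 combined, so a clear imbalance would be visible, though not adjusted for. The protocol's reactogenicity analysis (7.5) is descriptive, the sample size does not rest on these tests, and dose escalation follows event criteria. There is no formal primary hypothesis. All this stands and limits the importance of the point.

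Finally, age stratification could be mistaken for a cure for pooling controls over sequential cohorts. Step 8 shows that it is not.

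The case for naming the stratum survives. The tests remain undefined on this point until programming, and the obvious stratum is already used in both the randomisation and the ANCOVA.

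**Conclusion.** The point holds as a minor improvement. The Stage 2 CMH tests lack a stated stratum and, run as written, do not adjust for the age factor used in randomisation. The expected effect is small: a bias of about 1.5 points (0.5 to 3 over the assumed range) against an SE of about 7 points for a single reaction, and 0.9 to 1.3 points or less in 95% of cases if only chance imbalance is at work. The gain in power is about 2 percentage points in the one setting simulated. Larger error rates for the count test (0.19 to 0.35) arise only under extreme assumed shifts and should not be read as a forecast. All sizes rest on assumed age shares and reaction rates.

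**What to change.** In SAP 7.5.1, state that for Stage 2 Group 2 the CMH tests are stratified by age (65-74, 75-85). Apply this to the local reaction-count test, the systemic reaction-count test and the modridit severity test. Add a sentence saying that this adjusts for age only and does not remove other cohort or calendar-time differences that come from pooling PCV13.

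Optionally, add a sensitivity analysis stratified by age and cohort. It protects against those other differences but relies on the 33 concurrent controls, and simulated power falls from 0.90 to 0.62, so it should not replace the main test.

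The main change costs one extra variable in the table statement and showed no loss of power in the setting simulated. It needs no new data and no change to the design.

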7.5.2 Clinical Events

Clinical events capturing reactogenicity will be collected by the subject in the electronic daily diary. Specific local reactions requiring responses are pain, tenderness, redness/erythema, swelling, hardness, and induration at the immunization site. Systemic reactions are nausea, vomiting, diarrhea, headache, fever, tiredness (fatigue), myalgia/muscle pain, and arthralgia with grades 1-4 defined for each. Subjects in stage 1 will be asked to report joint pain/arthralgia through day 7 postimmunization during the day 7 visit. This addition was requested by the FDA after the electronic diary was being used at the sites. The ePRO device will be revised for Stage 2 so that subjects will be asked to report symptoms of arthralgia daily for 7 days post immunization. Additionally, elevated daily body temperature will be summarized by grade: grade 1 mild (100.4-101.1), grade 2 moderate (101.2 – 102.0), grade 3 severe (102.1 – 104) grade 4 potentially life threatening (>104).

Data will be summarized for each study day collected in the diary (day 1 thru day 7) by grade and overall. The number of subjects and percentage who experience each type of reaction will

be provided. The maximum grade for each type of reaction (number and percentage of subjects) will be provided.

At the Day 7 visit the investigator will assess each type of reactogenicity and based on the discussion with the subject will assess these as related or not. Those that are assessed as not related by the investigator will be excluded from a second table summarizing related reactogenicity events. The maximum grade for each type of related reaction (number and percentage of subjects) will be provided. In the event there are none judged as not related, this summary will not be produced.

7.5.3 Clinical Laboratory Evaluation

The baseline value is the last measurement taken prior to vaccine administration.

Quantitative clinical laboratory variables, i.e. hematology and biochemistry will be summarized using mean, standard deviation, minimum, maximum and median for each treatment group at each visit. Additionally, a within-subject change will be calculated as the post-baseline measurement minus the baseline measurement and summarized in the same way. Each laboratory result will be classified as low (L), normal (N), or high (H) at each visit according to the laboratory supplied reference ranges and laboratory data will be listed with flags for low or high.

Frequency tabulations of qualitative clinical laboratory variables (urinalysis) will be presented for treatment group (ASP3772 (1 μ g, 2 μ g, 5 μ g) or PCV13) and stage at each visit.

For hematology and biochemistry a summary of shifts (shift from normal or high to low, shift from normal or low to high) from baseline to worst finding during the treatment period will be presented for treatment group (ASP3772 (1 μ g, 2 μ g, 5 μ g) or PCV13) and stage.

The following data will be presented graphically by treatment group (ASP3772 (1 μ g, 2 μ g, 5 μ g) or PCV13) and stage:

- Box plot of Quantitative Laboratory Test Results will be displayed by treatment group (ASP3772 (1 μ g, 2 μ g, 5 μ g) or PCV13) and stage with PCV13 as a single group. The lower box will represent the 25th percentile, the middle line as the median, and the upper box the 75th percentile. A line showing the upper limit normal (ULN) and lower limit of normal (LLN) will be shown along with the minimum, maximum and outliers.
- Box plot of the maximum change from baseline for laboratory values will be displayed by treatment group (ASP3772 (1 μ g, 2 μ g, 5 μ g) or PCV13) and stage with PCV13 as a single group. A line showing the ULN and LLN will be shown. The lower box will be the 25th percentile, the upper box the 75th percentile, and the middle line the median. Minimum, maximum and outliers will be shown.

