1.3 Summary of Key Safety Information for Study Drugs

No clinical studies of ASP3772 have been conducted to date.

In the 5-cycle intramuscular dose toxicity study in rabbits (3772-TX-0001), a total of 5 intramuscular injections of ASP3772 at dose level of 5 µg of each PS per animal given once every 2 weeks to male and female New Zealand White rabbits over a period of 57 days was well-tolerated. There were no treatment-related effects on survival, clinical signs, skin reaction, body weight/food consumption, ophthalmology, hematology parameters, serum biotin, anti-biotin antibodies or organ weights. With the exception of the injection sites, there were no treatment-related macroscopic post-mortem or histopathological findings in the tissues/organs examined. Analysis of postdose sera confirmed that animals treated with ASP3772 had robust serum IgG antibody responses to all pneumococcal PS included in the ASP3772.

02 Dec 2019 Astellas Page 38 of 111

In animals treated with ASP3772, slightly elevated body temperature, changes in clinical pathology and histopathological findings at the injection sites were observed. The elevated body temperature and changes in clinical pathology such as reductions in prothrombin time and/or activated partial thromboplastin time, as well as increased fibringen concentrations, and decreased albumin and albumin/globulin ratio, and increased globulin, creatine kinase and C-reactive protein levels were considered to be consistent with the immune and/or inflammatory reactions induced by ASP3772 administration, which are expected responses in intramuscular immunization.

Microscopic findings at the intramuscular injection sites included ASP3772-related findings consisting of minimal to moderate myofiber degeneration/necrosis, minimal to mild histiocytic inflammation (muscle) and minimal histiocytic inflammation (subcutis), as well as ASP3772related exacerbation of local injection site findings that included minimal to moderate mixed cell inflammation (subcutis), minimal to marked mixed cell inflammation (muscle), minimal to mild mixed cell inflammation (dermis), minimal to moderate hemorrhage (subcutis), minimal to mild hemorrhage (muscle) and minimal serocellular crusts (epidermis). These changes recovered or tended to recover after a 4-week recovery period suggesting that the ASP3772related findings were reversible.

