6.2.1.2 Laboratory Values

Laboratory safety assessments will be collected at the screening visit and at study immunization if screening was performed > 7 days from study immunization [day 1]. Assessments will be repeated at follow-up visits on day 7 and day 30. These include the following:

- Hematology (hemoglobin, hematocrit, erythrocytes, leukocytes, differential WBC, platelets),
- Biochemistry (sodium, potassium, calcium, chloride, glucose, total cholesterol, triglycerides, blood urea nitrogen, creatinine, creatine kinase, uric acid, total protein, albumin, c-reactive protein),
- Coagulation profile (prothrombin time, activated partial thromboplastin time, fibrinogen)
- Hepatic profile (alkaline phosphatase, aspartate transaminase, alanine transaminase, γ -glutamyltransferase, total bilirubin, lactate dehydrogenase),
- Urinalysis (using dipstick - protein, glucose, pH, blood, leukocytes, urobilinogen, bilirubin, ketones, nitrite)
- Urine microscopy [optional] (casts, crystals, epithelial cells, leucocytes, erythrocytes, bacteria).
- Pregnancy Testing (Human Chorionic Gonadotropin (hCG))

Laboratory assessments assayed at baseline to determine eligibility are:

- Drug screening (amphetamines, barbiturates, benzodiazepines, cannabinoids and cocaine)
- Virology (Anti-HAV (IgM), HBsAG, Anti-HBc, Anti-HCV, Anti-HIV-1 and 2

Laboratory values collected on Days 7 and 30 will be categorized programmatically using the definitions in Appendix D: Grading Laboratory Abnormalities for Healthy Adult Subjects.

These post vaccination laboratory values are categorized into 4 grads of reactogenicity.

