10.4 Appendix D: Grading Laboratory Abnormalities for Healthy Adult Subjects

Clinical laboratory test results will be graded and displayed using these grades. Grading values are based on ICON Central Laboratories, and will be adjusted if the reference ranges change.

Chemistry	ICON Reference range	Mild (Grade 1)	Moderate (Grade 2)	Severe (Grade 3)	Potentially Life-threatening (Grade 4)†
Sodium – Hyponatremia (mEq/L)	136-145*	133 – 135	131 – 132	126 – 130	< 126
Sodium – Hypernatremia (mEq/L)		146 – 147	148 – 149	150 – 151	> 151
Potassium – Hypokalemia (mEq/L)	3.5-5.1*	3.3 – 3.4	3.1 – 3.2	2.9 – 3.0	< 2.9
Potassium – Hyperkalemia (mEq/L)		5.2 – 5.3	5.4 – 5.5	5.6 – 5.7	> 5.7
Glucose – Hypoglycemia (mg/dL)		60 – 64	50 – 59	40 – 49	< 40
Glucose – Hyperglycemia	Fasting 74-99	100 – 110	111 – 125	> 125	Insulin requirements or hyperosmolar coma
Fasting (mg/dL)					
Random (mg/dL)	Random 74-139	140 – 155	156 – 230	> 230	
Blood Urea Nitrogen (mg/dL)	7-19 (F) [18-50] 10-20 (F) [>50] 9-21 (M) [18-50] 8-26 (M) [>50]	22 – 25	26 – 30	> 30	Requires dialysis
Creatinine (mg/dL)	0.55-1.02 (F) 0.72-1.18 (M)	1.5 – 1.7	1.8 – 2.1	2.2 – 2.5	> 2.5 or requires dialysis
Calcium – Hypocalcemia (mg/dL)	8.4-10.2	7.9 – 8.3	7.4 – 7.8	6.9 – 7.3	< 6.9
Calcium – Hypercalcemia (mg/dL)		10.3 – 11.0	11.1 – 11.5	11.6 – 12.0	> 12.0
Magnesium – Hypomagnesemia (mg/dL)	1.3-2.1*	1.1-1.2	0.9 – 1.0	0.7 – 0.8	< 0.7
Phosphorous – Hypophosphatemia (mg/dL)	2.3-4.7	2.0 – 2.2	1.7 – 1.9	1.3 – 1.6	< 1.3
Creatine Kinase (mg/dL)	29-168 (F) 30-200 (M)	1.25 – 1.5 × ULN***	1.6 – 3.0 × ULN	3.1 – 10 × ULN	> 10 × ULN
Albumin – Hypoalbuminemia (g/dL)	3.5-5.0 [18-61] 3.4-4.8 [>61]	2.8 – 3.1	2.5 – 2.7	< 2.5	NA
Total Protein – Hypoproteinemia (g/dL)	6.4-8.3	5.5 – 6.0	5.0 – 5.4	< 5.0	NA
ALP (Increase by Factor)	40-150	1.1 – 2.0 × ULN	2.1 – 3.0 × ULN	3.1 – 10 × ULN	> 10 × ULN
Liver Function Tests – ALT (Increase by Factor)	≤55	1.1 – 2.5 × ULN	2.6 – 5.0 × ULN	5.1 – 10 × ULN	> 10 × ULN
Liver Function Tests – AST (Increase by Factor)	5-34	1.1 – 2.5 × ULN	2.6 – 5.0 × ULN	5.1 – 10 × ULN	> 10 × ULN
Bilirubin – When Accompanied by Any Increase in Liver Function Test (Increase by Factor)	≤1.20	1.1 – 1.25 × ULN	1.26 – 1.5 × ULN	1.51 – 1.75 × ULN	> 1.75 × ULN
Bilirubin – When Liver Function Test is Normal (Increase by Factor)	≤1.20	1.1 – 1.5 × ULN	1.6 – 2.0 × ULN	2.0 – 3.0 × ULN	> 3.0 × ULN

Table continued on next page

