Chemistry	ICON Reference range	Mild (Grade 1)	Moderate (Grade 2)	Severe (Grade 3)	Potentially Life-threatening (Grade 4)†
Total Cholesterol (mg/dL)	Desirable: < 200 mg/dL Borderline: 200 – 239 mg/dL High: ≥ 240 mg/dL	201 – 210	211 – 225	> 226	NA

* The laboratory values provided in the tables serve as guidelines and are dependent upon institutional normal parameters. Institutional normal reference ranges should be provided to demonstrate that they are appropriate.

** The clinical signs or symptoms associated with laboratory abnormalities might result in characterization of the laboratory abnormalities as Potentially Life Threatening (Grade 4). For example, a low sodium value that falls within a grade 3 parameter (125-129 mE/L) should be recorded as a grade 4 hyponatremia event if the subject had a new seizure associated with the low sodium value.

***ULN" is the upper limit of the normal range.

ALP: alkaline phosphatase; ALT: alanine aminotransferase; AST: aspartate aminotransferase; NA: not applicable; ULN: upper limit of normal

Hematology	ICON Reference range	Mild (Grade 1)	Moderate (Grade 2)	Severe (Grade 3)	Potentially Life-threatening (Grade 4)
Hemoglobin (Female Subjects) (g/dL)	11.5-15.5	10.0 – 10.9	8.5 – 9.9	7.0 – 8.4	< 7.0
Hemoglobin (Female Subjects) Change From Baseline Value (g/dL)		Any decrease – 1.5	1.6 – 2.0	2.1 – 5.0	> 5.0
Hemoglobin (Male Subjects) (g/dL)	13.2-17.0	11.4 – 12.4	10.0 – 11.3	8.0 – 9.9	< 8.0
Hemoglobin (Male Subjects) Change From Baseline Value (g/dL)		Any decrease – 1.5	1.6 – 2.0	2.1 – 5.0	> 5.0
White Blood Cell Increase (k/uL)	3.50-11.10*	11 – 15	15.1 – 20	20.1 – 25	> 25
White Blood Cell Decrease (k/uL)	3.50-11.10*	2.5 – 3.5	1.5 – 2.4	1 – 1.4	< 1
Lymphocytes Decrease (k/uL)	1.2-4.0	0.5 - 0.6	0.3 - 0.4	0.1 - 0.2	< 0.1
Neutrophils Decrease (k/uL)	1.8-7.0	1.3 - 1.6	0.8 - 1.2	0.5 - 0.7	< 0.5
Eosinophils (k/uL)	0.0-0.5	0.8 – 1.2	1.3 - 5	> 5	Hypereosinophilic
Platelets Decreased (k/uL)	150-400	125 – 140	100 – 124	25 – 99	< 25
Prothrombin Time (Increase by Factor)	11.4-14.9 sec	1.01 – 1.10 × ULN†	1.11 – 1.20 × ULN	1.21 – 1.25 × ULN	> 1.25 ULN
Partial Thromboplastin Time (Increase by Factor)	24.7-34.4 sec	1.01 – 1.2 × ULN	1.21 – 1.4 × ULN	1.41 – 1.5 × ULN	> 1.5 × ULN
Fibrinogen Increase (mg/dL)	228-439	476 – 600	601 – 700	> 700	NA
Fibrinogen Decrease (mg/dL)		150 – 199	125 – 149	100 – 124	< 100 or associated with gross bleeding or DIC

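### SAP 7.5.3 puts ULN and LLN lines on the box plot of laboratory change from baseline, where they have no meaning, and does not define *maximum change*; the flaw is confined to this one descriptive figure

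*SAP*

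**What the plan says.** SAP 7.5.3 (Clinical Laboratory Evaluation) lists two figures, each by treatment group and stage with PCV13 as one group.

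- The first is a box plot of measured results with ULN and LLN lines. That is coherent.
- The second is described as "Box plot of the maximum change from baseline for laboratory values will be displayed by treatment group". The same bullet states "A line showing the ULN and LLN will be shown".

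Earlier in the section, change is defined: "a within-subject change will be calculated as the post-baseline measurement minus the baseline measurement and summarized in the same way". It is therefore signed, and a fall is negative. SAP 6.2.1.2 sets the post-vaccination schedule: "Assessments will be repeated at follow-up visits on day 7 and day 30". For ASP3772 and PCV13 subjects, each maximum is thus normally taken over two changes. The SAP does not say whether it is the signed maximum or the largest magnitude, and it plans no matching plot of the minimum change.

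**The concern.** There are two separate faults.

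1. **Reference lines.** Limits for a measured level are drawn on an axis of differences. Someone scanning the figure for points outside the lines would take ordinary changes as below the LLN, and could take a true elevation as within limits. This holds whatever *maximum* means.
2. **Undefined summary.** If *maximum* is read literally on a signed change, it is the more positive of the Day 7 and Day 30 values. For analytes where a fall is the direction of concern, a transient fall at one visit would be replaced by the recovery at the other.

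Safety is the primary objective, and this is the only laboratory figure listed in SAP 7.5.3 that shows an extreme change per subject. It should be readable.

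**Working it through.** The documents give no figure of their own to reproduce here. The checks are a scale check, worked subjects and a small simulation.

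**Inputs.** Reference ranges are from SAP Appendix D:
- Platelets (row beginning "Platelets Decreased (k/uL"): 150–400 k/uL; Grade 1 decrease 125–140.
- Haemoglobin (row beginning "Hemoglobin (Female Subjects) (g/dL" and the matching male row): 11.5–15.5 g/dL female, 13.2–17.0 male.
- Albumin (row beginning "Albumin – Hypoalbuminemia (g/dL"): 3.5–5.0 g/dL at ages 18–61.
- ALT: up to 55; Grade 1 is 1.1–2.5 times the ULN.

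Subject values and visit SDs below are illustrative assumptions.

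**1. Scale check.** Change = post-baseline − baseline, so no change is 0. The largest rise possible within the normal range is ULN − LLN.

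| Analyte | LLN line | ULN line | ULN − LLN | Reaches LLN line? | Reaches ULN line? |
|---|---|---|---|---|---|
| Platelets | 150 | 400 | 250 | yes | no |
| Haemoglobin, female | 11.5 | 15.5 | 4.0 | no | no |
| Haemoglobin, male | 13.2 | 17.0 | 3.8 | no | no |
| Albumin, 18–61 | 3.5 | 5.0 | 1.5 | no | no |

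In every row, no change lies below the LLN line. For haemoglobin and albumin, even a rise across the whole normal range stays below it.

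ALT: 90 − 40 = +50, which is below the line at 55. The measured value is 90/55 = 1.64 times the ULN, which is Grade 1.

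**2. Worked subjects: signed maximum against largest magnitude.**

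| Baseline, Day 7, Day 30 | Changes | Signed maximum | Largest magnitude, with sign |
|---|---|---|---|
| Platelets 260, 135, 265 | −125, +5 | +5 | −125 |
| Haemoglobin (F) 13.0, 10.5, 13.1 | −2.5, +0.1 | +0.1 | −2.5 |
| Albumin 4.2, 2.9, 4.3 | −1.3, +0.1 | +0.1 | −1.3 |
| Platelets 220, 110, 180 | −110, −40 | −40 | −110 |

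The Day 7 platelet value of 135 in the first row is Grade 1. The last row shows that a persistent fall is attenuated under the signed reading, not erased.

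**3. Simulation of a fall at Day 7 only.** There were 200,000 subjects per setting, with independent normal visit errors. Assumed visit SDs were 15–30 k/uL for platelets, 0.4–0.8 g/dL for haemoglobin and 0.15–0.3 g/dL for albumin.

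- Across settings, 50–54% of subjects had a signed maximum at or above 0.
- For a platelet fall of 80, the median signed maximum was 0.0 to 0.4. The median minimum change was −79.9 to −80.3, and the median largest-magnitude change was about −80.
- At most 0.02% of platelet signed maxima reached the LLN line. None did for haemoglobin or albumin.

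**4. Offset with no vaccine effect, signed reading only.** For two equal-variance normal changes with correlation ρ, E[max] = SD × √((1 − ρ)/π). This gives 0.56, 0.40 and 0.31 SD of the change for assumed ρ of 0, 0.5 and 0.7.

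**The case against.** The misplaced lines are not open to dispute. The case against going further is strong, and most of it stands.

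**The signed reading is not stated.** A reader might infer that the figure, as specified, hides falls and shifts every analyte upward. The text supports only that it can. *Maximum change* may equally mean the largest change in either direction, and the shift summary in the same section looks to the worst finding in both directions. Under that reading the falls are shown. SAP 7.1 leaves figure formats to separate TLF specifications, which may settle the term.

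**Falls are reported elsewhere.** A reader might infer that the laboratory safety analysis misses them. It does not. SAP 7.5.3 tabulates change at each visit with its minimum, flags each result low, normal or high, tabulates shifts to low, and plots measured values with valid limits. SAP 7.5.3.1 and Appendix D grade decreases in platelets, neutrophils, haemoglobin and albumin, including haemoglobin decrease from baseline. The platelet value of 135 would be flagged low and counted as Grade 1. The ALT of 90 would be flagged high, counted as Grade 1 and plotted above the ULN on the first figure. One gap in the grade tables is that Appendix D grades prothrombin and partial thromboplastin times only for increases; the low flags still apply to them.

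**The offset is common to the groups.** A reader might infer a biased comparison with PCV13. With no vaccine effect, the same upward offset applies to every group, so it creates no spurious difference.

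**The nonclinical argument is thin.** Protocol 1.3 does report "decreased albumin and albumin/globulin ratio" in rabbits. The same section reports no treatment-related effect on haematology parameters and regards the clinical pathology changes as expected after intramuscular immunization. It does not support a specific concern about platelets or haemoglobin.

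**Conclusion.** The reference-line error is certain from the text and does not depend on any assumption about variability or on the meaning of *maximum*. Its size follows from the Appendix D ranges: the LLN line lies 150 k/uL above no change for platelets, and an ALT at 1.64 times the ULN can plot below the ULN line. This assumes that the Appendix D ranges are the limits drawn.

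The second fault is an ambiguity. A recovered Day 7 fall disappears from this figure only if *maximum* is signed, which the SAP neither states nor excludes. The simulation percentages and the 0.31–0.56 SD offset depend on that reading and on assumed SDs and correlations.

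Both faults are confined to one descriptive safety figure. No sample size, test or estimate depends on it. Protocol 12.8 uses graded laboratory results for dose escalation, and nothing in the documents links this plot to that decision. This is a low-severity correction, worth making because it is nearly free.

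**What to change.** In the second figure bullet of SAP 7.5.3:

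1. Replace the ULN and LLN lines with a reference line at zero. Keep ULN and LLN only on the box plot of measured values.
2. Replace the undefined *maximum change* with change from baseline at Day 7 and at Day 30, or with both the largest increase and the largest decrease per subject.

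In the simulated Day 7 platelet fall of 80, the largest-decrease version has a median of about −80, where the signed maximum has a median of about 0.

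The cost is two sentences in the SAP and one revised figure shell, with the TLF specifications brought into line. Data collection, sample size, alpha and clinical rules are unchanged.
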